### **5.6.1 Analysis Plans by Aim**

Aim 1 (Evaluation of the effect of SMAs and SMAs+P2P compared to usual care on diabetes patients' glycemic control, blood pressure, statin use, and insulin starts at 6 and 12-18 months post-enrollment): The primary analysis will be an intention to treat analysis (ITT) comparing all participants scheduled for an SMA (regardless of whether an SMA was actually attended) and eligible patients randomized to usual care. We also will conduct analyses comparing outcomes between the usual care group and: 1) The SMA Attendee group, defined as a subset of those in the SMA ITT group who attended at least one SMA; and 2) the SMA Engagement group, defined as the subset of patients who attended at least half of the SMAs offered in the series.

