We will conduct a "difference-in-differences" (DID) analysis on our primary A1c outcome using a multilevel linear mixed effect model. The model will include an indicator of treatment, an indicator for time, the treatment-time interaction (DID estimator), and variables to adjust for baseline A1c, age, gender, and race. Random intercepts to include will be for patients (level-1) nested within site (level-2). An identical analysis will be used for the secondary SBP outcome. In the secondary analyses of insulin and statin starts, we will implement a multilevel logistic regression model, and for anti-hypertensive medication class changes, we will implement a multilevel Poisson regression model. To analyze the 6- and 12-month differences in utilization measures between treatment groups, we will use a two-sample Mann-Whitney U test. Vargha and Delaney's A statistic will be used to describe the effect size of the Mann-Whitney test. As a robustness check, we will repeat the above analyses on a subset of patients who will be matched 1:1 based on propensity scores. The propensity score model will be developed using a logistic regression on the patient demographics. Although our initial analyses will use observed data, because we are relying on data available in the EHR, we anticipate more missing values than if this were an efficacy trial. Accordingly, we will use logistic regression to model patients' likelihood of having outcome data and defined strata within which outcome values were missing at random. We will then stratify patients according to these propensities and randomly sample from the observed outcome distribution and impute these values for missing data within each stratum. As a sensitivity analysis for the primary A1c outcome, we will impute the missing data such that any missing A1c measurements at 6 or 12 months will match the value at baseline.

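### The Attendee and Engagement comparisons with usual care select SMA patients on attendance after allocation, so they do not estimate an SMA effect and should be descriptive only

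*Combined protocol and SAP*

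**What the plan says.** Section 5.6.1, Aim 1, makes the primary analysis an intention-to-treat comparison, "comparing all participants scheduled for an SMA (regardless of whether an SMA was actually attended) and eligible patients randomized to usual care". It continues: "We also will conduct analyses comparing outcomes between the usual care group and" two further groups. The first is the "SMA Attendee group, defined as a subset of those in the SMA ITT group who attended at least one SMA". The second is "the SMA Engagement group, defined as the subset of patients who attended at least half of the SMAs offered in the series". The comparator in both is the usual-care group without restriction. The section does not call these analyses exploratory, descriptive or non-causal.

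The A1c model is a difference-in-differences mixed model with random intercepts for patient and site, and "variables to adjust for baseline A1c, age, gender, and race". As a robustness check, "we will repeat the above analyses on a subset of patients who will be matched 1:1 based on propensity scores". On the matching variables: "The propensity score model will be developed using a logistic regression on the patient demographics". No complier-average, instrumental-variable or attendance-weighted estimate is planned.

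Usual-care patients are a random sample of eligible patients who were not invited (Sections 5.1.1 and 5.2), and the study does not contact them (Section 5.3).

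**The concern.** Patients who are scheduled but do not come are removed from the SMA side only. The usual-care side keeps the patients who would not have come had they been scheduled. They cannot be taken out, because controls are never invited or contacted and their willingness to attend is never observed.

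Attending once, and still more attending half a series, may go with motivation, health, access to care and medication adherence. If attenders' A1c would have moved differently from non-attenders' under usual care, that difference is counted as an SMA effect.

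Two misreadings are at stake. A difference in either subset could be taken as the effect of SMAs on those who use them. A gradient from ITT to Attendee to Engagement could be taken as dose-response, although selection alone can produce one.

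**Working it through.** **Inputs from the plan (Section 5.6.2).** A1c difference of interest 0.5 points; SD of A1c change 1.45; worst-case ICC 0.10 in the SMA arm and 0 in controls; 10–16 groups per site with 8–14 people per group; at least 560 active patients and 560 controls.

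**The plan's own figures.** 10 groups × 7 sites × 8 people = 560, and 16 × 7 × 14 = 1,568. Both match, using the seven rows of Table 5. (The eight sites in the text would give 640 and 1,792; the bias below does not depend on this.) With 560 per arm, groups of 8, ICC 0.10 and an assumed two-sided 5% test, power for 0.5 points against usual care is 0.999. The stated 0.8 therefore holds as a minimum.

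**What the planned adjustments remove.**

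| Safeguard | Handles | Leaves |
|---|---|---|
| Difference-in-differences with patient intercepts | Stable differences in A1c level | A different A1c trend in attenders |
| Baseline A1c, age, gender, race | Differences explained by these | Motivation, adherence, access |
| 1:1 matching on demographics | Demographic imbalance | The same |

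**Bias formula.** Let p be the share of scheduled patients who attend, and d the amount by which attenders' A1c would fall more than non-attenders' under usual care. Suppose scheduled patients and controls are otherwise exchangeable. The whole usual-care group then averages over both types, and attenders do better than that average by d − pd. Hence

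attenders minus whole usual care = true effect in attenders + (1 − p)d.

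**Numbers.** The documents give neither p nor d. Assume p of 0.6–0.8, d of 0.2–0.5 and no true effect:

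| p | d = 0.2 | d = 0.3 | d = 0.5 |
|---|---|---|---|
| 0.8 | 0.04 | 0.06 | 0.10 |
| 0.7 | 0.06 | 0.09 | 0.15 |
| 0.6 | 0.08 | 0.12 | 0.20 |

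The range of 0.04–0.20 points is 8% to 40% of the 0.5-point difference of interest.

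**Effect on a test.** At the minimum design, 560p attenders remain, in groups averaging 8p. The standard error is 1.45 × √{[1 + (8p − 1) × 0.10]/(560p) + 1/560}.

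- p = 0.8: SE 0.105. With d = 0.2, a nominal 5% test rejects about 7% of the time.
- p = 0.6: SE 0.111. With d = 0.5, it rejects about 44% of the time.

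A simulation (70 groups of 8 against 560 controls, ICC 0.10, 1,000 runs) with p = 0.7, d = 0.3 and no effect gave an attender contrast of 0.089 in favour of SMA, against 0.09 from the formula. The ITT contrast was 0.001.

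**Engagement group.** Its share cannot exceed the Attendee share, so for the same d its bias is at least as large. With an assumed share of 0.3–0.5, the same d values give 0.5 × 0.2 = 0.10 to 0.7 × 0.5 = 0.35 points.

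**Is a complier-average estimate a safe replacement?** It divides the ITT contrast by p. If that contrast carries a bias b, the result with no true effect is b/p, which is 1.25b at p = 0.8 and 1.67b at p = 0.6. The attender contrast would carry b + (1 − p)d. The complier estimate is the more biased of the two when

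b/p > b + (1 − p)d, that is, when b > pd.

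Over the assumed ranges pd runs from 0.6 × 0.2 = 0.12 to 0.8 × 0.5 = 0.40 points. If b = 0, the complier estimate is unbiased, provided that being scheduled does nothing without attendance.

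**The case against.** **The primary analysis is ITT, and these comparisons are additional.** This stands. A reader might infer that the trial's main result is compromised or that the plan means to lead with the attender results. The documents support neither: ITT is named as primary regardless of attendance, and the other two are introduced as extra analyses. Reporting outcomes by exposure is also usual in an implementation trial.

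**The model is difference-in-differences with baseline adjustment.** This stands in part. Stable level differences are removed, so only a differential trend can bias the result. Nothing planned addresses such a trend.

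**Size and direction are assumed.** This stands. A reader might infer that the two analyses are known to favour SMAs. The documents contain no attendance rate and no comparison of attenders with non-attenders, so a better trend in attenders is plausible but not shown. The lack of comparability does not depend on its sign.

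**Attendance is not the only source of difference.** This also stands, and it limits the remedy. Scheduled patients were referred, or were invited and agreed, with decliners replaced, and they chose to join the study (Section 5.2). Controls were uninvited. The random sequence in Section 5.1.1 concerns SMA against SMA+P2P, not SMA against usual care. A reader might infer that two-stage least squares with arm as the instrument would put things right. It would do so only if scheduled patients and controls are exchangeable, which is doubtful here.

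**Conclusion.** The point holds for the two supporting comparisons only. As written, each sets a subset chosen on behaviour after allocation against an unrestricted usual-care group, and the planned model and matching do not repair this. Neither should be read as the effect of SMAs among attenders, nor the two together as dose-response.

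The figure of 0.04–0.20 A1c points rests on three assumptions: p of 0.6–0.8, d of 0.2–0.5 in favour of attenders, and scheduled patients and controls otherwise comparable. It illustrates what selection could do; it is not an estimate for this trial. The values for the Engagement group rest on a further assumed share.

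The primary ITT analysis is not affected by this point. Whether scheduled patients and controls are comparable to begin with is a separate question. It matters here because it rules out an instrumental-variable analysis as a straightforward replacement.

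**What to change.** In Section 5.6.1, Aim 1, replace the sentence that sets up the two comparisons with wording to this effect: *Outcomes in the SMA Attendee and SMA Engagement groups will be summarised descriptively. They will not be tested against usual care and will not be interpreted as treatment effects or as evidence of dose-response.* The propensity-matched repeat should then not be applied to these subsets as a test.

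A complier-average estimate on the full ITT sets may be added as a sensitivity analysis only, with arm as instrument, any attendance as exposure, the same covariates, and standard errors clustered by SMA group. The text should state that:

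- it assumes scheduling has no effect without attendance;
- it assumes scheduled and control patients are exchangeable, which is doubtful because the former were referred or agreed to attend and the latter were uninvited;
- any bias in the ITT contrast is multiplied by 1/p.

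The cost is a change of wording and, if wanted, one extra model. The trial gives up a formal test among attenders or, if the complier estimate is added, accepts a wider interval for it.

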### 5.6.2 Sample Size and Power Calculations

We chose five VA health systems (8 sites, as one healthy system will implement the program in 4 separate sites within the system) in which to implement SMAs + P2P based on our estimation of feasibility of implementation, given budget and time constraints. This number of health systems should also provide some variability in terms of the CFIR constructs (especially implementation context), which is important for investigating the role of these constructs in implementation success. We want to ensure that the study has a sample size sufficient to detect a clinically meaningful decline in A1c of 0.5% or a SBP decline of 5mm Hg between SMA and SMA+P2P. Based on discussions with clinical managers at a number of sites, both in relation to this project and others, they would be unlikely to undertake an addition of a new clinical management strategy unless it offered a benefit of this magnitude.

The clustering induced by the treatment in small groups requires that we account for the intra-class correlation within clusters in our sample size calculation. An increasing number of publications have started to provide estimates of ICCs from practice-based interventions. However, there are not good sources for estimates of ICCs of clinical intermediate outcomes induced by shared medical appointments. In a previous RCT conducted by us of P2P alone, which given the intimate nature of the pairing may represent an upper limit of induced correlation that might be found in a larger SMA, we found that the ICC was estimated at 0.10 but it was not significantly different from 0. Thus we used a range of 0 to 0.10 for the estimate of ICC of the outcome a1c or SBP measurement.

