We present sample size calculations using Satterthwaite's approximate F test using modified degrees of freedom rather than a t-test to calculate the power for trials and the number of clusters and cluster sizes required for the difference of means in the presence of clustering or differential clustering effects between study arms as described by Roberts (2005) and implemented by Batistatou and Roberts (2011). We estimate that we can conduct 10 to 16 SMA groups per site (equally distributed between SMA and SMA+P2P) with 8-14 people per group. At our low estimate of 10 SMA groups per site, we can detect an effect size of 0.5% decline in A1c with a power of 0.8 for all but the lowest number of participants per group (10) and highest ICC (0.1).

For the comparison of both SMA groups to inactive control we must take into account the differential ICC between groups as the inactive controls will have no clustering induced by the treatment and therefore will have an ICC of 0. We continue to assume a worst case scenario of an ICC of 0.10 in the intervention group. In this case we examine our ability to detect a difference of 5mm Hg in blood pressure between SMA groups and the inactive controls.

The standard deviation of a decline in A1c was estimated to be 1.45 from this same RCT mentioned in the paragraph above. The estimate of the standard error of the change in BP was estimated from a database of actual BPs obtained in routine clinical practice for 24,000 patients with diabetes and hypertension in one large service network in the VA over a 24 month period in FY 2004-2005. It depends on both the variation in BP change at the person level and variability within person between measurements. Increasing numbers of measurements in the 6 month window decreases the within person component of variance. Using the proposed 6 month pre- and post-intervention windows on either side of a 12-month intervention period we estimated the standard error for the change in blood pressure as 17 mmHg for the mean of 3 BP measurements that was observed in the sample for each of the pre and post periods.

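### The primary A1c model and the identical SBP model leave out the SMA group, although the sample size section plans for a group ICC of up to 0.10

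*Combined protocol and SAP*

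**What the plan says.** Section 5.6.1 (Aim 1) makes the pooled comparison of the SMA arms with usual care primary, by intention to treat, "comparing all participants scheduled for an SMA (regardless of whether an SMA was actually attended". A1c is analysed with a linear mixed difference-in-differences model: treatment, time, their interaction (the effect estimate), and "variables to adjust for baseline A1c, age, gender, and race". On the random part it says "Random intercepts to include will be for patients (level-1) nested within site (level-2". For blood pressure it adds "An identical analysis will be used for the secondary SBP outcome". Neither that section nor any other names a term for the SMA group, a group-by-time term or a cluster-robust variance.

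Section 5.6.2 takes the opposite view of the data. It says "The clustering induced by the treatment in small groups requires that we account for the intra-class correlation within clusters in our sample size calculation" and continues "Thus we used a range of 0 to 0.10 for the estimate of ICC of the outcome a1c or SBP measurement". For the comparison with usual care it says that "inactive controls will have no clustering induced by the treatment and therefore will have an ICC of 0" and, for the SMA side, "We continue to assume a worst case scenario of an ICC of 0.10 in the intervention group". It bases its power on a Satterthwaite-type test for clustering that differs between arms.

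**The concern.** The sample size allows for correlation within SMA groups, but the analysis does not. The power quoted in 5.6.2 therefore belongs to a test that 5.6.1 does not carry out.

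The two random intercepts cannot stand in for the missing term. Patient and site intercepts are constant over time and drop out of a change from baseline. The correlation at issue is change shared by patients treated together, which arises after the groups start. Each site is expected to run 10 to 16 groups, so site cannot represent group either.

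At stake are the p-value and interval of the primary comparison. Both would treat members of one SMA group as independent, so the interval would be too narrow and the false-positive rate above nominal.

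The same model has a smaller flaw: baseline A1c is both the time-0 outcome and a covariate.

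**Working it through.** **Inputs from 5.6.2.** ICC 0 to 0.10 in the SMA arms and 0 in usual care; 10 to 16 groups per site; m = 8 to 14 people per group; equal numbers of controls, minimum 560 + 560; SD of A1c change 1.45; 17 mmHg for SBP change (called a standard error there, used here as the per-patient SD of change); target differences 0.5% and 5 mmHg. **Assumed:** two-sided alpha 0.05.

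**The plan's own figures.** 7 × 10 × 8 = 560 and 7 × 16 × 14 = 1,568, so both totals reproduce with seven sites (the text of 5.6.2 says eight; that is a separate matter). Power at 560 + 560, m = 8, ICC 0.10, with clustering allowed for, is about 0.999 for A1c and 0.99 for SBP. This agrees with the plan's claim if its 0.8 is read as at least 0.8.

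**Variance ratio.** With two visits the interaction is a difference in mean change.

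- Design effect in the SMA arms: DE = 1 + (m − 1) × ICC; in usual care it is 1.
- With equal arms, true variance / model variance: R = (DE + 1)/2 = 1 + (m − 1) × ICC/2.
- Type I error = 2 × [1 − Φ(1.96/√R)].

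Example, m = 8, ICC 0.10: DE = 1.70, R = 1.35, 1.96/√1.35 = 1.687, error 9.2%.

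| ICC | m = 5 | m = 8 | m = 14 |
|---|---|---|---|
| 0 | 5.0% | 5.0% | 5.0% |
| 0.01 | 5.2% | 5.4% | 5.8% |
| 0.02 | 5.5% | 5.8% | 6.5% |
| 0.05 | 6.2% | 7.1% | 8.9% |
| 0.10 | 7.4% | 9.2% | 12.7% |

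The m = 5 column shows groups that are only partly analysed.

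**Standard errors at 560 + 560, ICC 0.10.** Model: SD × √(2/560). True: SD × √((DE + 1)/560).

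| Outcome | m | Model SE | True SE | Power for target |
|---|---|---|---|---|
| A1c | 8 | 0.087 | 0.101 | 0.999 |
| A1c | 14 | 0.087 | 0.111 | 0.994 |
| SBP (mmHg) | 8 | 1.02 | 1.18 | 0.989 |
| SBP (mmHg) | 14 | 1.02 | 1.31 | 0.969 |

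Power is Φ(target/true SE − 1.96). The model SE is 14% (m = 8) to 22% (m = 14) too small. The A1c significance limit is 1.96 × 0.0867 = 0.170 under the planned model. It should be 1.96 × 0.1007 = 0.197 (m = 8) to 1.96 × 0.1113 = 0.218 (m = 14).

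**Simulation.** With change scores, 20,000 replicates and ICC 0.10, the unadjusted test rejects a true null in 9.2% (m = 8) and 12.9% (m = 14). With the SMA group in the variance and Satterthwaite degrees of freedom it rejects in 4.7-5.2% across ICC 0 to 0.10.

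**Three visits.** Take a group share of 0.10 and residual variance 0.45 per visit, in units of the squared SD of change. The model variance for the contrast at one visit is 4(0.45 + 0.10/6)/n and the true variance is (4 × 0.45 + 0.10m)/n. The ratios are 1.39 (m = 8) and 1.71 (m = 14), giving 9.7% and 13.4%. If one post-baseline indicator pools the 6- and 12-month visits, simulation gives about 11-16%.

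**SMA versus SMA+P2P, if run.** Both arms are clustered, so R = DE, 1.70 to 2.30. At ICC 0.10 the error is 13.3% (m = 8) to 19.6% (m = 14).

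**Baseline used twice, no clustering, two visits.** Model/true variance = (3 + ρ)/4, where ρ is the baseline/follow-up correlation (assumed). With ρ = 0.5 the error is 6.7%; with ρ = 0.3 it is 7.5%. With three visits the effect is small.

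**The case against.** The strongest objection concerns size. The figure of 9-13% needs the top of the ICC range and fully analysed groups. The 0.10 comes from a trial of paired peers, which 5.6.2 says may be an upper limit for larger groups and which was not significantly different from 0. Research participation is optional, record linkage needs a signed authorization, and missing record data are expected, so fewer than 8 to 14 per group may be analysed. Scheduled patients who never attend share no group experience, which dilutes the correlation further; the documents give no basis for quantifying that. Even at the worst case, the significance window lies under half of the 0.5% target. At the 1,100 per arm ceiling in 5.1.3 it falls to about 0.121 to 0.141-0.156.

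All of this stands as a limit on size. It does not remove the omission: a non-significant ICC estimate is not evidence of zero, and the plan itself chose to protect against 0.10.

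Two further points. The exact percentage depends on how time is coded, which the plan leaves open, but the alternatives examined give larger figures, not smaller. Controls are sampled from each wave (5.2), so change common to a wave could partly cancel if wave were modelled. The plan does not model wave, and wave would not carry variation specific to one SMA group.

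**Conclusion.** The concern holds. The A1c and SBP models leave out a source of correlation that the same document treats as requiring allowance. For SMA versus usual care the false-positive rate runs from 5.0% at ICC 0 to 9.2-12.7% at ICC 0.10 with two visits, and somewhat higher with three. This rests on two-sided alpha 0.05 (assumed), equal arms, 8 to 14 analysed patients per group and clustering in the SMA arms only.

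Conclusions would change only for estimates near the significance limit; an observed difference of 0.5% would remain significant. It should be corrected before analysis, but it does not undermine the design. The double use of baseline A1c is minor and depends on a correlation that the documents do not give.

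**What to change.** In 5.6.1, for A1c and SBP, specify one of two approaches:

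- a random effect for SMA group acting on the post-baseline period, in the SMA arms only (group-by-time, partially nested), with Satterthwaite degrees of freedom; or
- cluster-robust standard errors by SMA group, with each usual-care patient as a cluster of one.

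A time-constant group intercept is not enough, because it largely cancels in the difference-in-differences. For the intention-to-treat set, define the cluster as the SMA group into which the patient was scheduled, including non-attenders. Apply the same clustering to SMA versus SMA+P2P if that comparison is made. Use baseline A1c once: either as the time-0 outcome, or as a covariate for the 6- and 12-month values. The remaining outcomes also need a method that respects SMA group, but the plan gives no ICC for them, so no size can be stated.

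The cost is a wording change and one variance term. The scheduled group must be in the analysis dataset. Section 5.2 describes scheduling patients into particular SMAs, so it should be recoverable, but the documents do not say that it is kept. Intervals widen: at ICC 0.10 the standard error is 0.101/0.087 = 1.16 times (m = 8) to 0.111/0.087 = 1.28 times (m = 14) as large. Power remains far above the planned 0.8.

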treatments will be offered in a random sequence within site, providing the clusterized random assignment required for comparability of the two treatment arms. In a modification of the classical cluster randomized design, patients are not assigned to groups prior to the group randomization to treatment but are recruited from a population of eligible patients when the site is ready to run a new group. If patients are then selected differentially into the groups we will lose all the advantages of the randomization step. Thus patients will be randomly sampled for invitation from eligible patients and recruited for each wave of the group treatment with a standard script that is identical whether the group is SMA only or whether P2P will be offered as an additional optional part of the intervention. All invited patients will be told that they are being invited to participate in SMAs, provided a brief description of what the SMAs involve, and informed that some groups will also be offered an additional (optional) opportunity to participate in P2P as a supplement to the SMAs. All invited patients will also be told that they are being offered an additional (optional) opportunity to participate in this research study. Participation in the research study is not required to participate in the SMAs or SMAs + P2P.

The study population will consist of diabetes patients who have poor glycemic control. Because not all eligible patients will be able to be invited to participate in one of the two programs during the study period, we will also have a pool of eligible patients whom we can use for untreated controls. We will randomly pull a sample of patients from each site to serve in this group. Thus, the trial will compare outcomes across three different treatment groups: (1) usual care without SMAs, (2) SMAs; and (3) SMAs + P2P.

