### **VA Patients**

SMA and SMA+P2P groups – As *usual care*, some sites may only conduct one group at a time depending on variability of their resources over time, but all sites will conduct a number of groups over the study period and the two treatments will be offered in a random sequence within site. Patients are not assigned to groups, but are recruited from a population of eligible patients when the site is ready to run a new group. Thus patients will be randomly sampled for invitation from eligible patients and recruited for each wave of the group treatment with a standard script that is identical whether the group is SMA only or whether P2P will be offered as an additional optional part of the intervention. There will be two methods of recruitment: existing mechanisms and data pull.

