The patients who are invited but decline participation in the P2P (**declined participation group**) will be asked if they are willing to answer a few questions with a study team member. The responses will be recorded but there will be no link between the responses and the participant.

Of the patients receiving usual care who were randomly not selected for invitation SMAs (since in all the sites too many patients will be eligible for invitation than there are resources to accommodate over the study period), a random sample will be selected from each wave to be part of the **no intervention control group** under a waiver of informed consent.

Patients will receive a \$20 gift card upon completion of the baseline survey and a \$10 gift card will be mailed with both the 6 and 12-month survey. Additionally, Patients who participate in an interview will receive a \$10 gift card by mail.

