Again, we assume that we can conduct 10 to 16 SMA groups per site (equally distributed between SMA and SMA+P2P) with 8-14 people per group. At the maximum, this would give us 1,568 people in active treatment and an equal number of inactive controls. At the minimum, this would give us 560 people in active treatment and an equal number of inactive controls. In this scenario, at our low estimate of 10 SMA groups per site, we can detect an effect size of 5mm decline in SBP with a power of 0.8 across all our ranges of group size and ICC. In this scenario, we also have a power at 0.8 at all estimated ICCs to detect a 0.5% difference in A1c between the active treatment groups and controls.

Table 5 shows a snapshot of the number of eligible patients per site. Across all sites, we will recruit between 560 and 1,568 active treatment patients and an equal number of inactive controls.

**Table 5: Number of Patients with Diabetes\* with qualifying A1c\*\*, and Number of These Patients with and without Serious Mental Illness (SMI) or Substance Use Disorder (SUD) and with SBP>140**

Site	No. of Diabetes Patients	No. of Diabetes Patients without SMI or SUD	No. of Diabetes Patients with Qualifying A1c**	No. with Mean SBP>140 in Past 6 months
West Haven (Firm A)	3,748	306	397	187
Providence	5,466	636	794	105
Palo Alto	3,877	404	534	110
Livermore	1,212	156	168	88
Monterey	3,736	298	381	160
Sacramento	5,847	858	1,045	210
Ann Arbor	11,020	2,064	2,576	955

\*Source: VHA CWD (last updated 2015).

\*\*Patients less than 70 years old with A1c>7.5, for patients age 70 or above Ac1>8.0

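### The primary A1c model adjusts for site differences in A1c level but not in A1c change, and no active-to-control ratio is fixed within site

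*Combined protocol and SAP*

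**What the plan says.** Section 5.6.1 (Aim 1) makes the primary contrast an intention-to-treat one, "comparing all participants scheduled for an SMA (regardless of whether an SMA was actually attended) and eligible patients randomized to usual care". The model has treatment, time, "the treatment-time interaction (DID estimator), and variables to adjust for baseline A1c, age, gender, and race". Its random part is "Random intercepts to include will be for patients (level-1) nested within site (level-2". It lists no site-by-time term, site slope or wave term. The SBP outcome uses the same model. The robustness check is a 1:1 propensity match on demographics, and site is not named there.

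Site is a design stratum in two ways. For SMA versus SMA+P2P, "the two treatments will be offered in a random sequence within site" (section 5.2). For usual care, section 5.1.1 says "We will randomly pull a sample of patients from each site to serve in this group", and section 5.2 (Data Pull) adds that "a random sample will be selected from each wave to be part of the" no-intervention control group.

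The only statement of relative numbers is in section 5.6.2: "Across all sites, we will recruit between 560 and 1,568 active treatment patients and an equal number of inactive controls". No section gives a ratio within site or within wave. Section 5.1.1 expects more missing A1c values in usual care without SMAs.

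**The concern.** A DID analysis is meant to protect against differences in change over time that are not due to treatment. Formulary, staffing and case mix could make A1c drift differently from one clinic to another. If the active arm draws a larger share of its patients from some sites than the control arm does, those local drifts enter the primary estimate as an apparent SMA effect, and the reported SE does not allow for them. A reader who sees site in the model may think this is covered. It is covered for A1c level only.

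**Working it through.** **1. The plan's own figures.** With 10 to 16 groups per site and 8 to 14 people per group, 7 × 10 × 8 = 560 and 7 × 16 × 14 = 1,568. Both match section 5.6.2 and imply seven sites, as in Table 5. The eight sites named in the text would give 640 and 1,792.

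With SD 1.45 and ICC 0.10 in groups of 8, the design effect in the active arm is 1 + 7 × 0.10 = 1.7; it is 1 in controls. SE = 1.45 × √(1.7/560 + 1/560) = 0.101. Power for 0.5% is Φ(0.5/0.101 − 1.96) = 0.999, so the claimed 0.8 holds. The documents state no alpha; 0.05 two-sided is assumed throughout.

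**2. Why the site intercept drops out.** For patient i in site s, baseline and follow-up A1c share the same patient and site intercepts. Within-patient change removes both. With complete pre/post data, the treatment-by-time coefficient is therefore the crude difference in mean change. Simulated seven-site data (true effect 0; site intercepts entered as fixed, the limiting case of random ones) gave these estimates:

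| Allocation | Follow-up | Patient intercept only | Plus site intercepts | Plus site-by-time |
|---|---|---|---|---|
| Uneven | complete | −0.1031 | −0.1031 | 0.0722 |
| 1:1 in each site | complete | 0.0590 | 0.0590 | 0.0590 |
| Uneven | about 30% missing | −0.1719 | −0.1738 | −0.1334 |
| 1:1 in each site | about 30% missing | −0.0204 | −0.0141 | −0.0449 |

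The crude DID in the first row was also −0.1031. A separate generalised least squares fit with random patient and random site intercepts gave 0.04823, again equal to the crude difference.

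**3. Bias.** Bias = Σ over sites of (share of active arm − share of control arm) × site trend. If the shares are equal in every site, it is zero whatever the trends. For independent site trends with SD τ, the bias has SD L × τ, where L is the root sum of squared share differences. Type I error = 2 × [1 − Φ(1.96 × SE / √(SE² + L²τ²))].

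*Moderately uneven (assumed).* Active counts are 60, 65, 70, 80, 90, 95, 100 (total 560) and control counts are the same in reverse. L = √[2 × (40² + 30² + 20²)]/560 = 76.2/560 = 0.136.

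*Controls following the Table 5 pool (assumed).* The pool without SMI or SUD is 306 + 636 + 404 + 156 + 298 + 858 + 2,064 = 4,722. Ann Arbor supplies 2,064/4,722 = 44% of controls, against 1/7 = 14% of active patients if these are equal per site. The squared share differences sum to 0.116, so L = 0.34.

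With SE 0.101:

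| τ (assumed) | Type I, L = 0.136 | Type I, L = 0.34 |
|---|---|---|
| 0.1 | 5.2% | 6% |
| 0.2 | 5.9% | 10% |
| 0.3 | 6.9% | 17% |

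**4. Cost of adjusting.** In the pool scenario there are 80 active patients per site and control counts c = 560 × pool share (about 18 at Livermore, 245 at Ann Arbor). Weight each site's difference in proportion to 80c/(80 + c), with variance 1.45² × (1.7/80 + 1/c). The SE becomes 0.109, and power is Φ(0.5/0.109 − 1.96) = 0.996. At 1:1 in every site the SE stays at 0.101.

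**The case against.** The strongest reply is that no bias follows from the documents. Controls are sampled from each site and each wave, and the totals are equal, so a roughly constant ratio is a natural reading; the bias is then zero. That stands. A reader might infer that the primary estimate is biased as planned, but the documents do not support this, because they neither state nor exclude a constant ratio.

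The size also depends on choices the plan does not make. Nothing says controls will follow the pool, and no between-site trend SD is given. About 75% of the squared share difference comes from Ann Arbor alone. If Ann Arbor ran the maximum 16 × 14 = 224 and the other six sites 80 each (704 in all), Ann Arbor's active share would be 32%, L would fall to 0.18, and type I error at 704 per arm would be 5.4%, 6.8% and 9.2%. At 1,100 per arm, equal active numbers with pool-proportional controls and τ = 0.3 would give about a quarter (SE 1.45 × √(2.7/1,100) = 0.072). That joins the most uneven allocation considered to the largest assumed trend, and should not be read as an expected error rate.

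Two other strong readings fail. Site is not ignored, since its A1c level is modelled. The randomised within-site sequence ("treatments will be offered in a random sequence within site, providing the clusterized random assignment") concerns SMA versus SMA+P2P. The primary contrast with usual care rests on sampling uninvited patients by site and wave.

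What remains is that a constant ratio may be hard to hold. Livermore's pool is 156, while 1,100 active patients spread over seven sites need 157 each. Section 5.2 says every site has more eligible patients than places, and Table 5 is a snapshot with lists re-pulled quarterly, so this is a risk only. Uneven loss of follow-up A1c could also unbalance the analysed set after an even draw.

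**Conclusion.** The gap is real and conditional. The primary model leaves site differences in A1c change unadjusted, the same holds for SBP, and the demographics-only propensity match does not repair it. Bias requires an active-to-control ratio, or A1c availability, that varies by site. With a constant ratio and even follow-up it is zero. Under assumed trend SDs of 0.1 to 0.3 points, type I error is about 5% to 7% for moderately uneven ratios and about 6% to 17% at 560 per arm (ICC 0.10) in the pool-proportional scenario, which is an illustrative upper case. These figures rest on the assumed trend SDs, ratios and 5% two-sided alpha, none of which is in the documents. Exact cancellation also needs complete data; with about 30% missing, the site intercept moved the simulated estimates by only 0.002 to 0.006. The change is worth making because it costs so little and protects the primary contrast.

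**What to change.** - In section 5.6.1, add site-by-time terms to the A1c model and to the identical SBP model.
- Add site to the propensity-score model.
- In sections 5.1.1 and 5.2, where the pool allows, draw controls at a constant ratio to scheduled SMA patients within site and wave, and report the ratio achieved by site.
- Use one site count throughout: Table 5 lists seven and the text says eight.

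Replacing random with fixed site intercepts, and adding wave-by-time terms, are optional. If wave means each SMA series (10 to 16 per site), the latter would add many terms.

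The model change costs a few degrees of freedom among at least 1,120 patients and an SE rise from about 0.101 to at most 0.109, with power for 0.5% still above 0.99. The constant-ratio draw is a procedural change to control selection as well as a change of wording. If controls have already been drawn, the model terms alone still remove the site-trend bias.
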